5.1.8 Pain

A pre-operative assessment of bilateral leg and back pain will be made to establish a baseline for comparison to postoperative results. Right leg, left leg and back pain will be evaluated by the patient using a 100 mm Visual Analog Scale (VAS). The VAS consists of three horizontal lines, one each for the right leg, left leg and back. The patient denotes his/her pain level by placing a vertical line along its length. To qualify for the study, one leg VAS score must be equal to or greater than 40 mm as measured and recorded by the clinical staff on the VAS questionnaire document.

5.1.9 Quality of Life

The patient's quality of life information will be captured using the SF-36 Quality of Life questionnaire. This questionnaire is to be completed by the patient.

5.2 Randomization Procedure

Patients will be randomly assigned on a two to one (2:1) basis to either the treatment or control group. Randomization will be stratified by clinical center and permuted block randomization will be performed within strata. The block size will be variable and randomly chosen from small multiples of 3. The randomization schedules for the study will be prepared in advance by the study statistician or designee. Investigational sites and the Sponsor will not have access to the randomization schedules.

Treatment assignments will be provided by the statistician for each site completed either by sealed envelopes or an electronic web-based program. If envelopes are used, they will be sealed and sequentially numbered with one envelope per patient. Once distributed to the sites, they will remain sealed until a prospective patient had passed all study criteria. The study coordinator or designee will open the envelope to determine treatment assignment prior to the procedure, allowing sufficient time for insurance authorization. The assignment card will be attached to the Case Report Form. Patient will be blinded to treatment until after the procedure.

Alternatively, a web-based randomization program may be utilized by sites where treatment assignment is made after verification of proper informed consent execution and study eligibility.

Any patient consented, whether randomized or not, will be assigned a patient number. The reason for failure to randomize or failure to treat will be recorded in his/her study records.

If a randomized patient is withdrawn prior to treatment, the next patient will be assigned the next randomly determined treatment as per the study randomization plan until a sufficient number of patients have been treated for each group.

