All patients screened for this study should be recorded but only consented patients will receive a study number. All consented patients will be assigned a unique patient number where the first two digits represent the investigative site and the last three digits represent the patient number (e.g. 01-001 represents the first consented patient at site 01). Patients are considered enrolled only after they have signed the informed consent and met all eligibility requirements. Patients will be identified by this assigned number for the duration of their participation in the study.

Randomization will be performed on a per-patient basis, blocked by center to maintain a 2:1 mix of patients in the investigational and control groups at each institution. Randomization must occur prior to surgery and only after the patient provides written informed consent, completes all baseline procedures and meets the requirements of the study inclusion and exclusion criteria. Sites are reminded that enough time should remain between randomization and surgery to allow sufficient time for insurance authorization.

As specified earlier, each Investigational Site may complete up to two training cases in advance of randomizing patients into the study. These cases provide an opportunity for the Investigator to become familiar with the technique and instrumentation. Training cases will not be randomized but will be followed per the protocol and analyzed as a separate population.

Any patient enrolled, whether randomized or not, will be assigned a patient number. The reason for failure to randomize or failure to treat will be recorded in his/her study records. For enrolled (consented & eligible) patients who **are not** treated, the following information will be recorded in the patient's study file:

- Demographic information
- Inclusion/exclusion criteria
- Reason for failure to randomize

If a randomized patient is withdrawn prior to treatment, the next patient will be assigned the next randomly determined treatment as per the study randomization plan until a sufficient number of patients have been treated per each group.

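### Section 5.2 lets sites hold unopened assignments in envelopes, and the protocol discloses the blocking rule to staff who see past assignments; the web program already in the plan should be the only method

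*Combined protocol and SAP*

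**What the plan says.** Section 5.2 (Randomization Procedure) sets the scheme: "Patients will be randomly assigned on a two to one (2:1) basis to either the treatment or control group". It adds: "Randomization will be stratified by clinical center and permuted block randomization will be performed within strata". On block size: "The block size will be variable and randomly chosen from small multiples of 3". Section 8.3 repeats that block sizes vary at random. Section 4.0 says randomization is "blocked by center to maintain a 2:1 mix of patients in the investigational and control groups at each institution". The protocol's opening page states that the document is for investigators and their representatives.

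On access, Section 5.2 says: "Investigational sites and the Sponsor will not have access to the randomization schedules". It then allows two methods of issue.

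- **Envelopes.** "If envelopes are used, they will be sealed and sequentially numbered with one envelope per patient". They go to the site and are to stay sealed until the patient has met all criteria. "The study coordinator or designee will open the envelope to determine treatment assignment prior to the procedure, allowing sufficient time for insurance authorization". The card is then attached to the case report form.
- **Web.** "Alternatively, a web-based randomization program may be utilized by sites where treatment assignment is made after verification of proper informed consent execution and study eligibility".

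Section 4.0 requires consent, completed baseline procedures and eligibility before randomization, whichever method is used. Only the patient is blinded, and only until after the procedure (5.2). A patient randomized but withdrawn before surgery begins counts as a screen failure (4.0). The ITT set holds randomized patients in whom surgery is attempted (8.1).

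**The concern.** Concealment means that whoever decides on entry cannot know or guess the next assignment. Two routes are open here.

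The first is custody. Unopened numbered envelopes at a site are its next assignments in order. The visible text does not mention opacity, tamper evidence, an opening log, an off-site check before opening, or return and reconciliation of unused envelopes. Concealment therefore rests on the seal and on site discipline.

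The second is guessing. The coordinator opens the card and the surgeon performs the procedure, so staff know the site's past assignments. The protocol they hold also gives the blocking rule and the within-site balance.

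Foreknowledge could matter because some entry decisions are judgements: being a candidate for full facetectomy or for fusion (4.1.1), and the disc height determined by the investigator (5.1.4). Selection of this kind would enter the AFRS minus fusion success difference directly, and that difference is judged against a margin of 0.15 (0.10 in the accrual rule, 8.3). The exclusion from ITT of patients withdrawn before surgery adds weight: the analysis set already depends partly on decisions made with the assignment known, so protection before assignment counts for more.

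**Working it through.** The plan gives no figure for predictability, so there is none to reproduce.

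**Inputs from the documents:** 2:1 allocation in permuted blocks within site, with random block sizes divisible by 3 (5.2); up to 30 sites and 300 to 750 patients (3.1), so on average 300/30 = 10 to 750/30 = 25 per site if all 30 are used; margin 0.15 (8.3).

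**Assumptions, because the documents are silent or the text is redacted:** block sets {3,6} or {3,6,9} with sizes equally likely; an observer who knows the set and every past assignment at the site, but not the realised block sizes; control success of 50-70%; a one-sided 5% criterion.

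**Step 1: predictability.** Site sequences were simulated. At each patient, P(next is AFRS) was computed from the exact posterior over the remaining block contents. Always guessing AFRS is right 2/3 = 66.7% of the time.

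| Block set | Correct, n=10 / n=25 | Certain, n=10 / n=25 |
|---|---|---|
| {3,6} | 74.2% / 75.0% | 8.0% / 9.5% |
| {3,6,9} | 72.4% / 73.2% | 2.8% / 3.3% |
| {6} fixed | 72.0% / 74.1% | 20% / 28% |
| {6,9} | 71.8% / 72.5% | 6.0% / 5.4% |
| {6,9,12} | 70.3% / 71.3% | 1.4% / 2.3% |

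For {3,6} and {3,6,9} the gain over the naive guess is about 6 to 8 points, and certainty is uncommon. Random block sizes do most of the protecting.

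**Step 2: illustrative bias from guessing.** Suppose a patient enrolled when P(AFRS) is above 2/3 has a success chance 5 points higher, and one enrolled when it is below 2/3 has a chance 5 points lower.

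Bias = 5 × (mean sign among AFRS patients − mean sign among control patients).

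This gives 3.3-4.1 points if every site steers. At 20% of sites: 0.20 × 3.3 = 0.7 and 0.20 × 4.1 = 0.8 points.

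**Step 3: false non-inferiority rate.** At a true difference of −0.15, rate = 1 − Φ(1.645 − bias/SE).

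- N=300 (200:100), control 60%, AFRS 45%: SE = √(0.45×0.55/200 + 0.60×0.40/100) = 0.0603. Bias 0.007 gives 6.3%; bias 0.008 gives 6.5%.
- N=750 (500:250): SE = 0.0603/√2.5 = 0.0381. The same biases give 7.2% and 7.6%.
- Over control success of 50-70%, the ranges are 6.3-6.6% and 7.2-7.7%.

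This is a fixed-sample normal approximation. It ignores the Bayesian predictions and the interim looks.

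**Step 4: what each change does.** Web assignment removes unopened assignments from the site, but the Step 1 figures stay the same while the blocks stay. Dropping size 3 can backfire: {3,6,9} to {6,9} raises certainty from about 3% to 5-6%, and {3,6} to fixed 6 raises it from 8-10% to 20-28%.

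**The case against.** Sealed, numbered envelopes with random within-site blocks are a recognised method, and the plan has more safeguards than a quick reading suggests. Consent and eligibility must precede assignment under both methods, and the web sentence does not say that anyone off-site verifies them either. The card on the case report form leaves an audit trail, although only after opening. Section 8.9 plans treatment-by-site comparisons of selected baseline variables, a site-by-treatment test on the primary outcome, and analyses with and without discrepant centers. These could flag some measured imbalance; they would not reveal or correct selection on unmeasured factors. All of this stands, and it limits the point.

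Two stronger readings are tempting. A reader might infer that a site holds its whole sequence and can read it. The documents do not say how many envelopes a site holds at once, and reading one ahead would break the plan's own rule that they stay sealed. A reader might also attach much larger error rates. If the next assignment were known for 20% of patients, the same 5-point steering would give 0.20 × 10 = 2 points, and a 5% rate would become about 9-10% at N=300 and 13-14% at N=750. Those figures belong to tampering, which nothing in the documents indicates.

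The guessing figures are themselves generous to the concern. They assume exact tracking from the first patient, steering on any departure from 2/3, and steering always in favour of AFRS.

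**Conclusion.** The point holds as a cheap improvement, not as a demonstrated flaw. Where envelopes are used, future assignments sit in site custody with few described controls, and the protocol gives staff who know past assignments more of the blocking rule than they need. Under the assumed block sets, best guessing is right about 72-75% of the time against 66.7%, and about 3-10% of assignments are certain. With 5-point steering at one site in five, a nominal one-sided 5% false-claim rate becomes about 6-8%. The bias is possible, not shown. Its size rests on the assumed block sets, steering effect, share of sites and 5% criterion, none of which the visible text supplies.

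**What to change.** 1. In Section 5.2, make the web-based program the only method for all remaining patients. It should record consent and eligibility, then issue one time-stamped assignment per patient number.
2. Have unused envelopes returned to the statistician and reconciled by number.
3. Move the block-size sentence (5.2) and the per-institution balance wording (4.0) to a restricted document held by the statistician. The effect is limited for investigators who have already read them.
4. Keep 2:1 allocation, stratification by site and randomly varying blocks. Do not simply drop size 3.

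Items 1 and 2 close the envelope route. They do not by themselves reduce guessing; item 3 addresses that only in part.

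The cost is a wording amendment, web set-up at sites still using envelopes, and retrieval of unused envelopes. No extra patients or study procedures are needed.

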5.3 Operative Procedure

Following the surgery, details of the surgical procedure are documented including:

- Operative date, time, clinical site location, investigator performing surgery
- Treatment assigned, device used and traceability
- Vertebral levels treated, decompression performed, procedure and instrumentation time, blood loss
- Source of bone for fusion
- Antibiotics and/or deep vein thrombosis prophylaxis used pre-, intra-, and/or post-operatively, if applicable
- Intra-operative complications

Immediately following surgery, the patient is transported to the surgical recovery area and monitored according to the hospital/physician protocol for surgeries of this nature. The patient may be released from the recovery room to the nursing unit when s/he has met the

hospital's criteria for discharge from the recovery area. Immediate postoperative care will be dictated by the hospital or physician's standard care protocol regarding post-anesthesia recovery. Patients shall be encouraged to ambulate after surgery as soon as is medically reasonable.

Unforeseen events (findings or procedures) may occur during decompression/spinal preparation procedure(s) prior to implantation of the ACADIA® Facet Replacement System or Control System. These unforeseen events are those that are not planned as part of this surgery (eg, a drop in oxygen saturation intraoperatively, evidence of an acute myocardial infarction, allergic reaction to an antibiotic, etc). Unforeseen events that are emergent in nature should be recorded as AEs and the investigator should reassess the patient's suitability for continued participation in this study.

If an intraoperative decision is made to perform a procedure other than what was intended for study enrollment, the patient will be withdrawn from the study and will be followed for safety as a separate "Not Treated" cohort. If a randomized patient is withdrawn prior to treatment, the next patient will be assigned the next randomly determined treatment as per the study randomization plan until a sufficient number of patients have been treated per each group.

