3.2.2 Patient Population

The AFRS Study will include patients as specified in the Inclusion/Exclusion criteria. Study patients will have lateral, lateral recess and/or central stenosis at a single level from L3 to S1 requiring decompression and facetectomy. Detailed enrollment criteria can be found in the Patient Selection section of this Protocol.

Patients will receive either the investigational or control treatment, using a posterior approach through a midline incision to treat lateral, lateral recess and/or central canal stenosis. All patients will receive a decompression and complete facetectomy. The operative level will receive either the test or control treatment. Up to two adjacent additional levels may be treated through decompression as required to treat stenosis that does not result in complete facetectomy or fusion.

Patients randomized into the investigational group will receive the AFRS device. Those randomized to the control group will receive an instrumented posterolateral fusion.

If the assigned device cannot be placed in the patient during the surgical procedure, this patient will be considered a treatment failure. This patient should receive treatment at the discretion of the principal investigator and must be followed per the protocol through hospital discharge and/or the resolution of any procedure-related adverse events that have occurred.

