8.0 STATISTICAL ANALYSIS PLAN

8.1 Analysis Populations

Primary Analysis Population:

The principal analysis of the primary and secondary endpoints will utilize the intent-to-treat (ITT) patient population. The ITT population will include all randomized subjects for whom surgery is attempted. Subjects for whom surgery is attempted but not successfully completed will be considered treatment failures. Randomized subjects in whom surgery is not attempted will be described in detail in a separate section of the study report.

Secondary Analysis Populations:

The primary and secondary objectives will be further analyzed using an as-treated (AT) analysis performed on all randomized subjects according to the treatment actually received.

The primary and secondary objectives will be further analyzed using a per protocol (PP) analysis performed on an evaluable patient population. The evaluable population will consist of all ITT subjects that: [1] meet critical study eligibility criteria and have no significant protocol deviations based on Clinical Events Committee assessment; [2] have the assigned procedure completed; and [3] completed the 24-month follow-up assessment.

Training Population:

This patient population will include all non-randomized AFRS treated patients enrolled during the pivotal phase of the trial as training cases at the site. A maximum of two patients per site for a total of 60 patients will be included in this cohort. Training cases will be described separately from randomized patients in the final study report and will be presented primarily using descriptive statistics. This patient population will be used to understand the learning curve in the use of the device by assessing the results of the Training cases relative to those obtained in the Treatment group arm of the randomized study.

An additional presentation of the safety data in which all of the patients treated with the AFRS device (non-randomized and randomized) are combined as one cohort and compared to the control group will be included.

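### Section 5.3 withdraws a patient whose procedure is changed during surgery, while Sections 8.1 and 3.2.2 make such a patient a treatment failure; nothing visible says which rule governs the primary analysis

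*Combined protocol and SAP*

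**What the plan says.** All references are to the combined protocol and SAP.

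- **Section 5.3.** If a decision is made during surgery to "perform a procedure other than what was intended for study enrollment, the patient will be withdrawn from the study", with safety follow-up in a separate cohort labelled Not Treated. The paragraph before it concerns unforeseen events that "may occur during decompression/spinal preparation procedure(s) prior to implantation". The sentence after it passes the next random assignment to the next patient when someone is withdrawn before treatment. It does not say whether a patient converted during surgery counts as such a case.
- **Section 3.2.2.** "If the assigned device cannot be placed in the patient during the surgical procedure, this patient will be considered a treatment failure". The same section describes the study surgery in both arms: "All patients will receive a decompression and complete facetectomy".
- **Section 8.1.** The primary set is defined by attempt: "The ITT population will include all randomized subjects for whom surgery is attempted". On operations that were started but not finished, the rule is: "Subjects for whom surgery is attempted but not successfully completed will be considered treatment failures". A third group is set apart: "Randomized subjects in whom surgery is not attempted will be described in detail in a separate section of the study report". The secondary as-treated analysis is an "analysis performed on all randomized subjects according to the treatment actually received".
- **Section 4.0.** A randomized patient can leave as a screen failure only before surgical procedures start. Removal from the study is limited to consent withdrawn before treatment, or no treatment attempted.
- **Sections 8.4 and 8.6.** A failure at an interim state is carried to 2 years with certainty. Any other subject without a 2-year outcome has it predicted, including a subject with no interim data.

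**The concern.** A patient whose operation is changed on the table is out of the study under 5.3 and an ITT failure under 8.1. Sites work from 5.3 and would record a withdrawal; the statistician works from 8.1.

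Two things could then go wrong. The patient could be moved to the group that 8.1 describes separately, because the Not Treated label resembles surgery not attempted and the visible text does not define an attempt. Or the patient could stay in ITT coded as withdrawn, with no 6- or 12-month data, and be given a predicted 2-year outcome with some chance of success. Section 3.2.2 requires follow-up of a patient whose device could not be placed only to discharge and/or resolution of procedure-related events, so missing interim data is likely.

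Either route alters the count of failures in a non-inferiority comparison with a 15-point margin. If the choice is left open, it may be made after outcomes are known.

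**Working it through.** **Step 1: does the narrow reading of 5.3 remove the conflict?** One could limit 5.3 to events before implantation.

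- The withdrawal sentence carries no such limit.
- The preceding paragraph places its events during decompression or spinal preparation. Section 3.2.2 makes decompression part of the study surgery in both arms, so surgery has begun.
- Section 4.0 closes the screen-failure exit once surgical procedures begin.
- Section 8.1 turns on surgery being attempted, not on a device being implanted.

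The conflict with 8.1 and 3.2.2 therefore remains.

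**Step 2: what would dropping these patients do?** The plan states no figure for this, so there is none to reproduce. From the documents: a margin of 0.15 (Section 8.3), 2:1 allocation, and a minimum of 300 = 200 + 100 and maximum of 750 = 500 + 250 patients. Assumed: success with conversions counted as failures of p_T = 0.55 (AFRS) and p_C = 0.70 (control), which lies exactly at the margin; conversion rates c_T and c_C; a single look; and one-sided 5% or 2.5% error, because the win threshold is redacted.

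Success among retained patients is p/(1 - c), so

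shift = [p_T/(1 - c_T) - p_C/(1 - c_C)] - (p_T - p_C)

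error = Φ(shift/SE - z), with z = 1.645 or 1.960, unpooled SE, and n = n_T(1 - c_T) and n_C(1 - c_C).

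*5% versus 1% at 200:100* (10 AFRS patients and 1 control patient dropped): 0.55/0.95 = 0.5789 and 0.70/0.99 = 0.7071. Shift = 0.5789 - 0.7071 + 0.15 = +0.0219 (unrounded). SE = √(0.5789 × 0.4211/190 + 0.7071 × 0.2929/99) = 0.0581. Shift/SE = 0.377, so error = Φ(-1.268) = 10.2% and Φ(-1.583) = 5.7%.

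*5% versus 5% at 200:100*: 0.5789 - 0.7368 + 0.15 = -0.0079; SE = 0.0577; error 3.7% and 1.8%.

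| Conversions, AFRS vs control | Shift (points) | Error at nominal 5% / 2.5%, 200:100 | Same, 500:250 |
|---|---|---|---|
| 3% vs 1% | +1.0 | 7.0% / 3.7% | 8.5% / 4.6% |
| 5% vs 1% | +2.2 | 10.2% / 5.7% | 14.7% / 8.6% |
| 5% vs 5% | -0.8 | 3.7% / 1.8% | 3.1% / 1.5% |
| 1% vs 3% | -1.6 | 2.7% / 1.3% | not tabulated |

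Varying assumed success from 0.45 vs 0.60 to 0.65 vs 0.80 at 200:100, the 5% vs 1% case gives 8.8% to 12.7% at nominal 5% and 4.7% to 7.2% at nominal 2.5%.

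**Step 3: when does the sign change?** The shift equals p_T·c_T/(1 - c_T) - p_C·c_C/(1 - c_C). For small rates it is zero when c_T/c_C is about p_C/p_T, which is 0.70/0.55 = 1.27 here (exactly 1.269 at c_C = 1% and 1.256 at c_C = 5%). Over the range of assumed success above it runs from 0.60/0.45 = 1.33 to 0.80/0.65 = 1.23. With equal success it is 1.0, and equal conversion rates then shift nothing. The direction depends on conversion rates and success rates together.

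**The case against.** The strongest reply is that 5.3 governs conduct and 8.1 governs analysis. Section 8.1 depends on surgery being attempted, not on continued participation, so an analyst who applies it counts these patients as failures whatever the site recorded, and the prediction route requires passing over its explicit failure rule. This has force: 8.1 is a usable rule. It does not settle the matter, because the visible text does not define an attempt, 8.1 has its own group for surgery not attempted, and the 5.3 label points towards that group. Text after the primary endpoint and in the win-analysis section is redacted, so a reconciling rule may exist there; none is visible.

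A second reply concerns Section 4.0. A reader might infer that it also makes these patients failures. It does not mention failure. Its limit on removal is also arguable: if treatment means the implant or the fusion, a patient diverted during decompression has had none attempted. That objection stands, and the point rests on 8.1 and 3.2.2, with 4.0 supporting only the boundary for screen failures.

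A third reply is that the raised error rates need an imbalance that nothing in the documents supports. That also stands. Section 9.1 expects procedural complication rates similar to other posterior fixation procedures. It speaks of complications, not conversions, but it gives no ground for assuming more conversions with AFRS.

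**Conclusion.** The contradiction is real and can be shown from the text alone: Section 5.3 withdraws patients whom 8.1 and 3.2.2 count as failures. It should be fixed.

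Its effect is not established. A reader might infer that 5.3 biases the trial towards non-inferiority, or inflates its error rate. The documents do not support that: they give no conversion rates, and the shift takes either sign. Under the assumed 0.55 versus 0.70 success, the single-look error at nominal 2.5% and 200:100 moves up to 5.7% (5% vs 1%) or down to 1.8% (5% vs 5%). These are illustrations that do not model the multi-look Bayesian design. A reader might also take 1.27 as a general threshold; it belongs to those assumed success rates only.

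**What to change.** Reconcile 5.3 with 8.1 and 3.2.2 for the analysis:

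1. State that a randomized patient in whom surgery was begun, and whose assigned procedure was changed or not completed, stays in the ITT population in the assigned arm. At every look this patient is in the failure state that 8.4 carries to 2 years, and is not predicted under 8.4 or 8.6. The qualifier matters: without it, every operated patient would be a failure.
2. Define attempted surgery in 8.1 to match.
3. State that the replacement rule for patients withdrawn before treatment does not apply to them.
4. State their place in the as-treated analysis.
5. Report them by assigned arm, with the reason.

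Clinical management of these patients is left to the sponsor.

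The cost is a few sentences and one table. No new data are needed: Section 5.3 already records the treatment assigned and the device used, and Section 5.2 the reason for failure to treat. The drawback is a slightly lower success rate in the arm with more conversions.
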